#### 4.5 Multiple Comparisons

As this is a first-in-human study, there are no statistical hypotheses being tested.

#### 4.6 Data Derivations and Transformations

All data derivations are for efficacy data. Therefore, information in this section pertain only to Protocol VC02-101.

#### 4.6.1 C-peptide AUC0-4h and AUC0-2h

Area under the curve (AUC) is calculated by adding the areas under the curve between each pair of consecutive observations. The calculation is based on the trapezoidal rule:

$$AUC = \frac{1}{2} \int_{i=1}^{n-1} (t_{i+1} - t_i) (y_i + y_{i+1})$$

Where there are n C-peptide measurements  $y_i$  at nominal time points  $t_i$  (i=0,...,n-1), and  $(t_i+1-t_i)$  will be measured in hours.

Specifically,

$$\begin{aligned} AUC_{0-4h} &= 0.5(y_0 + y_{0.5})/2 + 0.5(y_{0.5} + y_1)/2 + 0.5(y_1 + y_{1.5})/2 + 0.5(y_{1.5} + y_2)/2 \\ &+ 1(y_2 + y_3)/2 + 1(y_3 + y_4)/2 \end{aligned}$$

$$AUC_{0-2h} = 0.5(y_0 + y_{0.5})/2 + 0.5(y_{0.5} + y_1)/2 + 0.5(y_1 + y_{1.5})/2 + 0.5(y_{1.5} + y_2)/2$$

After Implantation Visit 3, 2-hour MMTTs will be conducted at Visit 7 (Week 8), Visit 8 (Week 12), Visit 9 (Week 16), Visit 10 (Week 20), Visit 12 (Week 39), Visit 14 (Week 65), and Visit 16 (Week 91). After Implantation Visit 3, 4-hour MMTTs will be conducted at Visit 11 (Week 26), Visit 13 (Week 52), Visit 15 (Week 78) and Visit 17 (Week 104 or Early Termination). For subjects with an immeasurable C-peptide ( $\leq 0.1$  ng/mL) as determined by the simplified oral glucose challenge test, the AUC of the respective 2-hour MMTT will be set to 0. C-peptide results reported as  $\leq 0.1$  ng/mL will be imputed as 0 for determination of the AUC0-4h and AUC0-2h.

An unscheduled time point measurement will be mapped to be a scheduled time point measurement for AUC calculation if: 1) A scheduled time point measurement is missing; and 2) The time of the unscheduled sample collection is within a 10-minute sampling window for that scheduled time point except for the last scheduled time point. Specifically, within 10 minutes after the start time of Boost Hi-Protein drink for the 0 minute time point; between 20 and 40 minutes after the 0 minute time point sampling, for the 30 minute time point; between 50 and 70 minutes after the 0 minute time point sampling, for the 60 minute time point; between 80 and 100 minutes after the 0 minute time point sampling, for the 90 minute time point; between 110 and 130 minutes after the 0 minute time point sampling, for the 120 minute time point; and between 170 and 190 minutes after the 0 minute time point sampling, for the 180 minute time point. If the last scheduled time point (120 minute time point for a 2-hour MMTT or 240 minute time point for a 4-hour MMTT) is missing and if there is an unscheduled time point that is after the last scheduled time point, the unscheduled measurement will be mapped to be the last time point measurement. For example, if the 240 minute time point is missing for a 4-hour MMTT, but there is a measurement at 270 minutes, then the measurement from the 270 minute time point will be used, with a time point value of 240 minutes.

After the mapping of unscheduled time point measurement(s), if any C-peptide measurement is

still missing, the imputation rules specified in Section 4.4 will be applied.

Baseline 4-hour MMTT is defined as the 4-hour MMTT performed during the Screening period. Similarly, baseline 2-hour MMTT is defined as the 2-hour MMTT (the first 2 hours) from the 4-hour MMTT performed during the Screening period.

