18 MAY 2020

	V1 a Screen	V2 Screen	V3 Enroll	V4	V5	V6	V7	V8	V9	V10	V11	V12	V13	V14	V15	V16	V17 or ET	V18 Follow- Up
Assessments	Wk -5	Wk -4	Day 1	Day 2	Wk 2	Wk 4	Wk 8	Wk 12	Wk 16	Wk 20	Wk 26	Wk 39	Wk 52	Wk 65	Wk 78	Wk 91	Wk 104	Wk 105
Ultrasound - Safety Evaluation							Х		Х		Х		Х		Х		Х	
Ultrasound - Pre-Explant a						X (ti	me-poi	ints TB	D bas	sed on	expla	nt pro	cedure	es)			Х	
Video and Photos b			X		Х	(additio	nal tin	ne-poin	ts TB	D bas	ed on	explan	it proc	edures	;)		Х	
AE and Concomitant Medications		Х	Х	X	Х	Х	X	Х	X	Х	X	X	X	X	X	Х	Х	Х
ICD for Follow-Up Study c																		Х
Central Laboratory Tests or S	Study-Prov	ided Testin	ng Kits	•			•											
Drug Screen d	X		X															
HBsAg, HCV, HIV	X																	
CMV IgG and IgM g		Х											Х				Х	
CMV PCR		Х						Х			Х							
EBV IgG	X																	
Hematology & Chemistry	X	Х	X		Х	Х	Х	Х	Х	Х	Х	Х	Х	X	Х	Х	Х	
HbA1c	X		X						Х		Х		Х		Х		Х	
Follicular Stimulating Hormone	Х																	
Urine Pregnancy Test e	X		X										Х				Х	
Thyroid Stimulating Hormone f	Х																	
Quantiferon TB	Х																	
SOGCT C-peptide	Х																	
Ultrasensitive C-peptideh		Х					Х	Х	Х	Х	Х	Х	Х					

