#### 4.2.2. Exclusion Criteria

The following exclusion criteria are applicable to all subjects. Subjects presenting with any of the following will not be included in the trial.

Diabetes-specific:

- 1. A detectable stimulated serum C-peptide at any time-point during the screening period, defined as >0.2 ng/mL (>0.0667 nmol/L).
- 2. Current use of any oral anti-diabetic medication.
- 3. Medical history of islet cell, kidney, and/or pancreas transplant.
- 4. Occurrence of six or more severe hypoglycemic events within six months of enrollment.
- 5. Known causes of diabetes other than T1DM.
- 6. Diabetic complications such as:
  - a. Kidney disease (Stage 3 to 5),

- Renal dysfunction (macroalbuminuria defined as protein of 2+ or greater on dipstick, MDRD eGFR <60 mL/min/1.73m^2)
- c. Proliferative retinopathy (active or untreated)
- d. Diabetic foot ulcers
- e. Amputations attributable to diabetes
- f. Severe peripheral neuropathy.
- 7. Hemoglobin A1C level of  $\geq 10.0\%$ .
- 8. Non-compliance with current anti-diabetic regimen.

Medical History:

- 9. Significant skin conditions involving the area(s) targeted for implantation. Examples include but are not limited to recurrent boils/furuncles, extensive surgery or scarring, or lipodystrophy.
- 10. Uncontrolled or untreated thyroid disease or adrenal insufficiency.
- 11. Active alcohol abuse or history of alcohol abuse within five (5) years of enrollment.
- 12. Positive urine drug screen for substances of abuse during the screening period or history of drug abuse within five (5) years of enrollment. Medical marijuana use may be allowed by the PI after consultation with the Medical Monitor and/or Sponsor.
- 13. Prior history of malignancy with the exception of:
  - a. Basal cell carcinoma of the skin;
  - b. Squamous cell carcinoma of the skin that has been recurrence free for  $\geq$  five years;
  - c. Appropriately treated in situ carcinoma of the cervix.
- 14. Known allergies to portions of the cellular excipients used as cell preservation solution or the PEC-01 manufacturing process (i.e., bovine, porcine allergies).
- 15. History of severe asthma or COPD.
- 16. BMI  $\geq$  32 kg/m^2 or <18 kg/m^2 at screening.
- 17. Active hepatobiliary disease or an AST or ALT >1.5 x ULN at screening or a total bilirubin >1.5 x ULN unless the subject has a history of Gilbert's disease.
- 18. Active infection or known history of Hepatitis B or C.

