# 6.17. Unplanned or Unscheduled Visits

Unplanned visits may occur at any time for reasons of subject safety and/or collection of additional time-point data. Possible reasons for unplanned visits include but are not limited to:

- Laboratory testing to evaluate immunosuppression drug levels.
- Adverse event follow-up.
- Abnormal laboratory test follow-up.
- Review of blood sugar values with possible exogenous insulin dose adjustments.
- Additional pre-operative evaluations.
- Post-implant and/ or explant site evaluation (includes evaluation of incision healing).
- Suture removal post-procedure.
- Repeat or follow-up ultrasound evaluations (safety or location).

- Explant of a VC-02-300 unit or sentinel unit.
- Perform an SOGCT or MMTT.
- Obtain video and/or photos of an explantation procedure.
- Administration of immunosuppression drugs

Source documentation should reflect the occurrence of all Unplanned Visits. Data may be collected from these visits depending on the procedures conducted. A subject may need to be in a fasted state for Unplanned Visits depending on the laboratory tests required. (e.g., lipid panel or MMTT).

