### 7.2.2. 2-Hour Mixed Meal Tolerance Test

The 2-hour MMTT is conducted during Visit 7 (Week 8), Visit 8 (Week 12), Visit 9 (Week 16), Visit 10 (Week 20), Visit 12 (Week 39), and Visit 14 (Week 65), and Visit 16 (Week 91). In addition to the time = 0 collection, samples for glucose and C-peptide are also collected at 30, 60, 90, and 120 minutes after the start of the Boost® meal test.

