# 7.3. Simplified Oral Glucose Challenge Test (SOGCT)

All subjects complete the SOGCT at Visit 1 to confirm a stimulated C-peptide level >0.2 ng/mL is not presented (per the exclusion eligibility criterion). After all other required fasting blood and urine samples for the visit have been collected, a fasting C-peptide sample is collected and at time = 0 the subject then drinks Boost® Hi-Protein (volume equal to 6 mL/kg body weight to a maximum of 360 mL). The entire drink must be ingested within 15 minutes. The second C-peptide sample is then collected at any time between 30 to 60 minutes after the start of the SOGCT.

[figure not shown]

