## 6.2 Secondary Efficacy Endpoints and Analyses

Each of the secondary efficacy endpoints will be analyzed using an  $\alpha = 0.05$  level of significance. Given the large number of secondary efficacy endpoints, the p-values for these endpoints will be considered descriptive.

For all secondary efficacy analyses, the FAS (Cohort 2 subjects who meet the FAS criteria) will be used. Change from baseline in C-peptide AUC0-4h following an MMTT at Weeks 52, 78, and 104 and change from baseline in C-peptide AUC0-2h following an MMTT at Weeks 8, 12, 16, 20, 39, 52, 65, 78, 91, and 104 will be analyzed in a similar manner to the ANCOVA performed for change from baseline in C-peptide AUC0-4h at Week 26, with the relevant baseline as the covariate. For subjects who continue to have a C-peptide  $\leq 0.1$  ng/mL as determined by the simplified oral glucose challenge test, the AUC of the respective 2-hour MMTT will be set to 0. A listing of the 2-hr MMTT/C-Peptide and Glucose results will be provided, as well as a listing of the simplified oral glucose challenge.

Time to onset of biological response of C-peptide following MMTT will be assessed using Kaplan-Meier (KM) product-limit method, with the p-value from the logrank test also provided.

The number and percent of subjects achieving a positive stimulated C-peptide (defined as > 0.2 ng/mL) after implant will be analyzed using Fisher's exact test. The number and percent of subjects in each treatment group and the p-value from the Fisher's test will be provided (at each time point, where appropriate).

Change from baseline in frequency of hypoglycemic events (24-hour; daytime [start between 6 a.m. -12 a.m.]; nocturnal [start between 12 a.m. -6 a.m.]) at Weeks 16, 26, 52, 78 will be analyzed using ANCOVA, with treatment group as a factor and the relevant baseline as a covariate. This analysis will be performed using HEs from both the patient-reported diary and from CGM. A listing of hypoglycemic events will be provided for both patient-reported data and from CGM data.

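### The SAP sets the AUC of a 2-hour MMTT to 0 from an SOGCT result, but the only scheduled SOGCT is before implant and none is paired with any 2-hour MMTT

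*SAP*

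**What the plan says.** SAP 4.6.1 lists the post-implant 2-hour and 4-hour MMTTs. For subjects with an immeasurable C-peptide (0.1 ng/mL or below) it then says: "as determined by the simplified oral glucose challenge test, the AUC of the respective 2-hour MMTT will be set to 0". The next sentence is a separate rule at sample level: each C-peptide result of 0.1 ng/mL or below counts as 0 in the AUC.

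SAP 6.2 repeats the SOGCT rule for the secondary analyses. It opens "For subjects who continue to have a C-peptide" at or below 0.1 ng/mL and ends "the AUC of the respective 2-hour MMTT will be set to 0".

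On timing, Protocol 7.3 says "All subjects complete the SOGCT at Visit 1 to confirm a stimulated C-peptide level >0.2 ng/mL is not presented". In Protocol Table 1 the row "SOGCT C-peptide" has one mark, in the Visit 1 (Week -5) column, and SAP Appendix A shows the same. Protocol 7.2.2 places the other test after implant: "The 2-hour MMTT is conducted during Visit 7 (Week 8), Visit 8 (Week 12), Visit 9 (Week 16), Visit 10 (Week 20"), followed by Weeks 39, 65 and 91. A later SOGCT can arise only at an unplanned visit, where Protocol 6.17 lists "Perform an SOGCT or MMTT" among the possible reasons.

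**The concern.** The rule draws on a test that the schedule does not provide at the visits where the rule acts. The SAP does not say which SOGCT belongs to which 2-hour MMTT. It does not limit the rule to MMTTs that were not done, and it does not say that measured values take precedence. A programmer who follows the text could link the screening SOGCT to every later 2-hour MMTT and write zeros over measured post-implant C-peptide.

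At stake is the secondary endpoint of change from baseline in C-peptide AUC0-2h, which describes how early and how far C-peptide rises after implant. Zeros written over measured values would bias that description downward. They would also contradict other results: SAP 4.6.2 counts a C-peptide above 0.2 ng/mL in an MMTT as a biological response, so a subject could be a responder and have AUC0-2h of 0 from the same test.

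**Working it through.** **1. The plan's own figure.** SAP 4.6.1 uses the trapezoidal rule with samples at 0, 0.5, 1, 1.5, 2, 3 and 4 h. SAP 10 says that 0.20 ng/mL corresponds to an AUC of 0.8 ng x h/mL over 4 hours.

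- 0-4 h at a flat 0.20: 4 x [0.5 x (0.2+0.2)/2] + 2 x [1 x (0.2+0.2)/2] = 0.4 + 0.4 = 0.8. This reproduces.
- 0-2 h at a flat 0.20: 4 x 0.1 = 0.4 ng x h/mL.

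**2. Schedule.**

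| Test | When | C-peptide samples |
|---|---|---|
| SOGCT | Visit 1 (Week -5) only | fasting, plus one at 30-60 min |
| 2-hour MMTT | Weeks 8, 12, 16, 20, 39, 65, 91 | 0, 30, 60, 90, 120 min |
| 4-hour MMTT | Week -4, then Weeks 26, 52, 78, 104 | 0, 30, 60, 90, 120, 180, 240 min |

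No SOGCT is scheduled with any 2-hour MMTT. SAP 6.2 analyses AUC0-2h at ten visits (Weeks 8, 12, 16, 20, 39, 52, 65, 78, 91, 104). Weeks 52, 78 and 104 use 4-hour MMTTs, which the rule does not name, so seven of the ten are exposed.

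**3. Literal reading (the Visit 1 SOGCT governs).** Protocol 4.2.2 excludes "A detectable stimulated serum C-peptide at any time-point during the screening period, defined as >0.2 ng/mL", so every eligible subject is at or below 0.2 ng/mL at screening. Some share f is at or below 0.1 ng/mL; the documents do not give f. For those subjects all seven 2-hour AUCs become 0. Take an assumed post-implant profile of 0.2, 0.3, 0.4, 0.5, 0.4 ng/mL:

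0.5 x (0.5 + 0.7 + 0.9 + 0.9)/2 = 0.75 ng x h/mL, set to 0.

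If zeroed subjects otherwise resemble the rest, the group mean falls to (1 - f) of its true value. For an assumed true mean of 0.75:

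| f | Reported mean AUC0-2h (ng x h/mL) |
|---|---|
| 25% | 0.56 |
| 50% | 0.38 |
| 75% | 0.19 |
| 100% | 0 |

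One subject's series could also run 0 at Week 39, measured at 52, 0 at 65, measured at 78, 0 at 91.

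**4. Paired reading (an SOGCT near each MMTT).** The rule has no scheduled input. It operates only after an unplanned SOGCT, where a fasting sample and one 30-60 minute sample would override five samples over 120 minutes. For an assumed late rise of 0, 0, 0, 0.3, 0.4 ng/mL:

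0 + 0 + 0.5 x (0+0.3)/2 + 0.5 x (0.3+0.4)/2 = 0.075 + 0.175 = 0.25 ng x h/mL, set to 0.

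**5. Is the rule needed for performed tests?** No. If all five samples are at or below 0.1 ng/mL, the sample-level rule makes each one 0 and the AUC is 0 without the SOGCT sentence.

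**The case against.** The wording works against the literal reading. *Respective* pairs an SOGCT with a given MMTT, and *continue to have* implies a repeat test after implant; a single Week -5 result fits neither. SAP 4.6.4 and 4.6.6.1 also drop days with an SOGCT from post-implant calculations, so the SAP's authors had later SOGCTs in mind. The sentence may therefore be inert in practice. This stands, and it is why the loss of all seven visits is a risk of one reading and not the expected result.

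The paired case is also hard to reach. Both tests start fasted with the same drink, and Protocol 6 and 6.17 list them as alternatives. The late-rise profile is assumed, and its 0.25 lies below the 0.4 that a flat 0.20 ng/mL gives. This stands as to likelihood. It does not supply the missing pairing or precedence rule.

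A reader might infer that the rule can only remove real signal. The documents do not support that. It may be meant to supply a value when an SOGCT is negative and the 2-hour MMTT was not done, in which case nothing measured is lost. The sample-level rule could not replace that use, because it needs MMTT samples.

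A reader might also infer that the baseline AUC0-2h would be zeroed and the change inflated. The rule follows a list of post-implant MMTTs, and *continue* points to later tests, so the text does not support this either.

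Finally, secondary p-values are descriptive, and SAP 6.2 plans listings of 2-hour MMTT and SOGCT results, so an overwritten value could be spotted. That softens the consequence but leaves the derivation undefined.

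**Conclusion.** The concern holds in a limited form. The rule does not match the schedule under either reading: literally it reaches back to a pre-implant test, and as a paired test it has no scheduled input. Because it states no precedence, following it as written can replace measured C-peptide with 0.

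The exposure is the secondary AUC0-2h analyses at Weeks 8, 12, 16, 20, 39, 65 and 91. The primary Week 26 AUC0-4h, AUC0-2h taken from 4-hour MMTTs, and the response endpoints based on C-peptide above 0.2 ng/mL are not touched. It would be wrong to infer that the primary efficacy result is at risk.

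The overall size cannot be established. It depends on the reading adopted, on the share at or below 0.1 ng/mL at screening, and on post-implant profiles, none of which the documents settle. The profiles and means above are illustrations.

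**What to change.** Preferred: delete the SOGCT sentence from SAP 4.6.1 and from SAP 6.2, and compute AUC0-2h from the MMTT samples with the existing rule that a result of 0.1 ng/mL or below counts as 0.

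Alternative, if the sponsor wants a value for a 2-hour MMTT that was not performed: restrict the rule to that case, require a post-implant SOGCT in the same visit window, and state that measured MMTT values always take precedence.

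Either change means editing two sentences before the AUC0-2h analyses are programmed. Deletion has one downside: a visit with a negative SOGCT and no MMTT would be missing instead of 0, because SAP 4.4 needs at least two timepoints for an evaluable MMTT and allows no other imputation.

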### 7.2. Mixed Meal Tolerance Test (MMTT)

MMTTs are conducted after all other vital signs evaluations and laboratory tests have been collected. The MMTT test should only be started if the subject has been fasting for at least eight

(8) hours. All MMTT supplies will be provided by the Sponsor or designee. Basal exogenous insulin will be continued during the test, but any short-acting insulin will be withheld starting four hours prior to starting the test. Prior to initiating the MMTT, the subject's fasting glucose will be tested at the site and the value must be within 70-200 mg/dL to begin the MMTT. If the fasting glucose is not initially within range, the site may recheck levels while the subject is still at the clinic. If the fasting glucose remains outside of the allowed range, the subject must return to the site within the visit window and attempt the MMTT again.

An intravenous catheter can be placed in a patent vein in the subject's arm for the collection of blood samples. Insertion of the catheter should occur at least 30 minutes prior to any blood collections on the days MMTTs are performed. The subject should sit upright during the test. Slow walking is permitted, but vigorous exercise should be avoided.

Baseline, fasting blood samples are drawn for glucose and C-peptide within approximately five minutes prior to the start of the meal test. At time = 0, the subject drinks Boost $\mathbb{R}$  Hi-Protein (volume equal to 6 mL/kg body weight to a maximum of 360 mL). The entire drink must be ingested within 15 minutes.

For any visits requiring both an MMTT and an explant procedure, it is acceptable to perform the MMTT on a separate day up to 5 days prior to the explant procedure. Further details regarding MMTTs may be outlined in the study reference manual.

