## 4.4 Handling of Dropouts or Missing Data

MMTTs will require a minimum of two timepoints in order to be considered evaluable. Any missing timepoints will be imputed using the following rules:

For C-peptide and blood glucose values:

- If the final timepoint is missing, it will be imputed as the average of the last available timepoint and zero (the value '0'). If consecutive, final timepoints are missing, this function will be performed twice (once for each timepoint).
- If a middle timepoint is missing, it will be imputed as the average the two neighboring timepoints. If consecutive, middle timepoints are missing, both values will be imputed as the average of the two closest, neighboring values on each side.

C-peptide value only:

- If the 0 minute timepoint is missing, the value will be imputed as zero (the value '0'). If multiple timepoints were missed at the start of an MMTT, the timepoints will be imputed in reverse order (starting with the latest missing timepoint). The missing timepoint(s) will be imputed as one-half the value of the subsequent timepoint. The 0 minute timepoint will be imputed as zero (the value '0').

Blood glucose value only:

If a first timepoint is missing, the value will be imputed as the average of the first available timepoint and zero (the value '0'). If multiple timepoints were missed at the start of an MMTT, the timepoints will be imputed using this same formula, in reverse order (starting with the latest missing timepoint and repeating for each subsequent missing value until the 0 minute timepoint has been imputed).

For AE dates where the start and/or end date are partial dates, the following rules will apply:

- If a month and year of an event is clearly after implant, then the dates will remain partial dates but the AEs will be indicated as treatment-emergent.
- For partial dates within the same month and year as the implant, if the site knows the event occurred prior to implant, then they enter "01" for the day. If the site knows the event occurred after implant, then they enter the last day of the month. Using these rules, the AEs will be correctly indicated as treatment-emergent or non-treatment-emergent.

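### When a scheduled MMTT sample is missing, SAP 4.6.1 cannot map an unscheduled pre-drink or slightly early final sample, so a usable value in the AUC is replaced by one imputed towards zero

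*SAP*

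**What the plan says.** Protocol 7.2 fixes the fasting draw before the meal: "Baseline, fasting blood samples are drawn for glucose and C-peptide within approximately five minutes prior to the start of the meal test". Protocol 7.2.1 and 7.2.2 time the later samples from the start of the drink.

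SAP 4.6.1 maps an unscheduled sample to a scheduled time only under a first condition, "A scheduled time point measurement is missing", and then only inside a window:

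- **0 minutes:** "within 10 minutes after the start time of Boost Hi-Protein drink for the 0 minute time point".
- **Inner points:** two-sided, for example "between 20 and 40 minutes after the 0 minute time point sampling, for the 30 minute time point". The list includes 110 to 130 minutes for the 120-minute point.
- **Last point (120 or 240 minutes):** excepted from the 10-minute window. Mapping happens "if there is an unscheduled time point that is after the last scheduled time point", with no upper limit. The SAP's example enters a 270-minute value as 240 minutes.

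What is still missing goes to SAP 4.4. A missing 0-minute C-peptide becomes zero. For the other end: "If the final timepoint is missing, it will be imputed as the average of the last available timepoint and zero".

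The resulting AUC0-4h at Week 26 is the Cohort 2 primary endpoint (SAP 6.1).

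**The concern.** At the start of the test, the substitution window lies on the opposite side of the drink from the draw that it replaces. A genuinely fasting unscheduled sample has no route into the AUC, while one taken during the first 10 minutes of drinking has. At the end, an unscheduled sample five minutes early has no mapping rule, while one thirty minutes late is used as if on time.

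In both cases a real measurement gives way to an imputed value that is usually too low. The subjects exposed are those with measurable C-peptide, who carry any efficacy signal.

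The 120-minute point adds an inconsistency. It is an inner point in a 4-hour test and the last point in a 2-hour test. Baseline AUC0-2h comes from the first two hours of the 4-hour screening test, whereas Weeks 8, 12, 16, 20, 39, 65 and 91 use 2-hour tests. The two terms of the AUC0-2h change may therefore follow different mapping rules.

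**Working it through.** **Inputs.** AUC formula and mapping rules: SAP 4.6.1. Imputation: SAP 4.4. Illustration of 0.20 ng/mL giving 0.8 ng x hour/mL: SAP 10. Sampling times 0, 30, 60, 90, 120, 180 and 240 minutes: Protocol 7.2.1.

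**Weights.** Collecting terms in the SAP's trapezoid for AUC0-4h, the weights on y0, y0.5, y1, y1.5, y2, y3, y4 are 0.25, 0.5, 0.5, 0.5, 0.75, 1.0, 0.5 (sum 4.0). For AUC0-2h they are 0.25, 0.5, 0.5, 0.5, 0.25 (sum 2.0).

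**The plan's own figure.** Flat 0.20 ng/mL: 0.20 x 4.0 = 0.80. This matches.

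**Error per affected 4-hour test.**

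- Start, y0 set to 0: error = -0.25 x y0. Flat: -0.25 x 0.20 = -0.05, and -0.05/0.80 = -6.25%.
- End, y4 set to y3/2: error = 0.5 x (y3/2 - y4). Flat: 0.5 x (0.10 - 0.20) = -0.05, again -6.25%.
- Both: -0.10/0.80 = -12.5%.

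The end error is negative whenever y4 exceeds half of y3. If the last available time point in SAP 4.4 is read to include the unmapped early sample, y4 becomes half of that sample, and the flat result is the same -6.25%.

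**2-hour test, flat 0.20 (AUC 0.40).** Start: -0.05/0.40 = -12.5%. End, if the 110-to-130-minute window does not apply: 0.25 x (0.10 - 0.20) = -0.025, and -0.025/0.40 = -6.25%. Both: -0.075/0.40 = -18.75%.

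**Range on assumed responder profiles.** The documents give no profiles; these are illustrations (ng/mL at the seven nominal times). The last two columns show the error from samples that the rule does accept: a +10-minute value used as fasting (linear between y0 and y0.5), and a 270-minute value used as 240 (the slope from 180 to 240 minutes continued).

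| Profile | AUC0-4h | Start | End | Both | +10 as 0 | 270 as 240 |
|---|---|---|---|---|---|---|
| .15 .2 .25 .3 .3 .25 .2 | 0.99 | -3.8% | -3.8% | -7.6% | +0.4% | -1.3% |
| .3 .5 .7 .8 .8 .6 .45 | 2.50 | -3.0% | -3.0% | -6.0% | +0.7% | -1.5% |
| .8 1.2 1.8 2.2 2.2 1.8 1.2 | 6.85 | -2.9% | -2.2% | -5.1% | +0.5% | -2.2% |
| 1 1.2 1.4 1.5 1.5 1.3 1.1 | 5.28 | -4.7% | -4.3% | -9.0% | +0.3% | -0.9% |

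On the flat profile both of the last two columns are 0%. Accepting a post-drink or late sample therefore costs less than imputing in every case shown except one tie (third profile, -2.2% either way).

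**Non-responders.** SAP 4.6.1 sets values at or below 0.1 ng/mL to 0. A subject with only such values has an AUC of 0 under any rule, so the error is zero.

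**The case against.** The strongest reply is that the rule is rarely reached. It needs a scheduled sample to be missing and a separate unscheduled one to exist. A reader might infer that any sample a few minutes off its time is refused. The documents do not support that. The AUC uses nominal times, and neither document sets a draw tolerance that would relabel a 240-minute sample taken at 235 minutes as unscheduled. Likewise, the draw about five minutes before the drink is itself the scheduled 0-minute sample and is used normally. This stands, and it limits the point to the double condition.

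A reader might also infer that the last-point rule is reversed, as the 0-minute rule is. It is not: late samples are kept, so the rule is one-sided and unbounded. Nor does the 120-minute problem reach every AUC0-2h. In 4-hour tests, which supply the baseline and Weeks 52, 78 and 104, a 115-minute sample is mapped. For 2-hour tests the text points both ways: the exception for the last point removes the window, while the list gives 110 to 130 minutes without limiting it to 4-hour tests.

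Finally, no hypothesis is tested, the primary output is a least squares mean and standard error, and all MMTT results are listed. These facts lower the stakes. They do not make the rule fit the protocol's fasting draw.

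**Conclusion.** The concern holds in a limited form. Where a scheduled sample is missing and an unscheduled one exists, SAP 4.6.1 cannot use a pre-drink sample for 0 minutes or a sample at 230 to 239 minutes for 240, and SAP 4.4 then supplies 0 or half the last available value. In an affected test, AUC0-4h falls by 6.25% at either end and 12.5% at both on the SAP's flat profile, and by 2.2% to 4.7% at one end or 5.1% to 9.0% at both on the assumed responder profiles. The both-ends figures need two missing scheduled samples and two unscheduled ones in the same test.

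A reader might take these percentages as bias in the Week 26 result. They are not: they are errors per affected test, the frequency is not given, and no effect on a group mean can be derived. The likely direction is downward after implant. Stimulated C-peptide above 0.2 ng/mL at screening is an exclusion, so baseline is low and the change score would tend to be understated. Whether the 120-minute rule differs between test lengths depends on how the exception for the last point is read. This is a wording correction worth making, not a threat to the trial's design.

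**What to change.** In SAP 4.6.1:

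1. For 0 minutes, accept an unscheduled sample drawn in the 10 minutes before the drink starts, and prefer it to any post-drink sample.
2. For the last time point, also accept unscheduled samples up to 10 minutes early (230 to 240 minutes, or 110 to 120 in 2-hour tests), and use the sample closest to nominal time.
3. State that the 110-to-130-minute window applies to the 120-minute point in both test lengths.

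Keep the present post-drink and late-sample mapping, including the 270-minute example, as a fallback when no better sample exists. Removing it would send those samples to SAP 4.4, where the error was larger in all but one of the cases worked above.

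With these changes the flat illustration returns to 0.80 when an unscheduled sample is available at the affected end. The cost is a few sentences of SAP wording and minor programming; no data collection changes.
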